6.1. Schedule of Study Procedures Table

Table 1. Schedule of Study Procedures

Procedures	Remote Screening Activities	Self Complete Activities	Remote Clinician Consult 1	Remote Clinician Consult 2	Remote Health Coach Interactions	Remote Supplemental Visit(s)
Eligibility	✓					✓ ^a
Informed Consent	✓					✓ ^a
ID Verification	✓					✓ ^a
Validated Tools		✓				
Non-Validated Surveys/ Questionnaires		✓				
Register for Verily Sleep Apnea (VSA) app/program		✓				
Medical and Sleep History Questionnaire		✓				
OSA Diagnostic Consult with Evaluating Clinician			✓			
Home Sleep Test (HST)		✓ ^b	✓ ^b			
Ship HST		✓				
PAP Therapy				✓		

Prescribed with Managing Clinician						
Verily Sleep Apnea (VSA) program PAP Therapy On-Boarding		✓				
Remote Interview					✓	✓
Compliance monitoring/outreach		✓			✓	✓
90-Day Compliance Check		✓			✓	
Adverse Event Evaluation	✓	✓	✓	✓	✓	✓
Protocol Deviation Assessment	✓	✓	✓	✓	✓	✓
Study Exit						✓
^a Administered if new version of the Informed Consent Form is released that impacts currently enrolled participants ^b HST may be administered more than once if test results are inconclusive						

6.2. Study Conduct and Procedures

The study is conducted in accordance with this clinical investigational plan and ethical principles consistent with GCP and applicable regulatory requirements to protect the rights, safety, and well-being of the study participants.

Prior to any study-related procedures, informed consent must be obtained.

6.2.1. Recruitment

Participants will be recruited through a variety of methods such as IRB-approved advertisements, registries, care provider recommendation, and community events. All volunteers will be directed to visit the Project Baseline website or a study phone line to learn more about the study. Volunteers can express an interest in joining the Baseline Sleep Apnea Study #2 by visiting the Project Baseline website (www.projectbaseline.com) and enrolling in the Project Baseline Community Study. The study may also be referred to as “Baseline Sleep Apnea Study”, “Sleep Apnea Study #2”, or “Sleep Apnea Study” on some recruitment material and other participants facing material.

6.2.2. Screening/Screen Failures

Participants will be screened through the Project Baseline Community Study through data collection defined in that protocol. Participants enrolled in the Project Baseline Community Study will complete survey questions used to assist with screening and enrollment (such as demographics) into the Baseline Sleep Apnea Study #2.

Participants who consented to participate in the Baseline Remote Health Study but do not meet one or more criteria required for participation in the study during screening will be considered screen failures.

This data will be documented on the appropriate case report form.

6.2.3. Enrollment

Participants who are enrolled in the Project Baseline Community Study may be enrolled in the Baseline Sleep Apnea Study #2 based on an assessment of the study eligibility and selection criteria. Study personnel will be provided with guidance regarding participant eligibility for study enrollment. Target distribution will be based on demographics (e.g. age, gender, socioeconomic status).

Participants who qualify for the study will be notified via the Member Portal, Verily Sleep Apnea (VSA) app, email, mail, phone, text, or other methods that they are eligible to participate. Participants will be considered enrolled in the study when they have signed the IRB approved Informed Consent documents and are determined to meet all eligibility criteria.

6.2.4. Participant Compensation

Participants may be incentivized for enrolling in the study. Participants will be compensated as described in the IRB-approved Informed Consent Form.

6.2.5. Visit Schedule

The Baseline Sleep Apnea Study #2 participant journey includes:

- Remote Screening Activities
- Self Complete Activities

[REDACTED]

Remote Screening Activities

Participants that appear to qualify for the Baseline Sleep Apnea Study #2 will be invited to complete remote screening activities. Proof of identity will be required prior to enrollment. Before enrollment and engaging in any study activities, participants will be asked to sign the IRB-approved electronic Informed Consent Form. Consent will be obtained by the Investigator or his/her delegate, if applicable by state law. An individual is considered to be enrolled in the study upon signature of the consent and confirmation of all eligibility criteria. All participants will be given a signed copy of the consent, or sent one via the Member Portal, email, mail, or other methods.

All consented participants in the Baseline Sleep Apnea Study #2 will be asked to undergo the assessments outlined in the Schedule of Study Procedures Table(s) and Test Procedures sections of the protocol.

Self Complete Activities

All consented participants in the Baseline Sleep Apnea Study #2 will be asked to undergo the self-completed activities outlined in the Schedule of Study Procedures Table(s) and Test Procedures sections of the protocol.

Compliance with self-complete activities will be assessed throughout the study and participants will receive targeted reminders about activities that need to be completed.

[REDACTED]

[REDACTED]

[REDACTED]

Remote Supplemental Visit(s) and Study Exit

Participants who do not complete study activities within the requested time frame may be contacted throughout the study duration to attend a supplemental remote visit. During these visits, additional interviews/surveys may be deployed to help understand issues,

non-compliance and improve compliance moving forward. The study team may also review device/app setup and troubleshooting to help participants if they become stuck. Additionally, the study team may reach out to the participant throughout the duration of the study via phone or email for troubleshooting.

The study team reserves the right to update the VSA app as needed throughout the course of the study (e.g., to fix newly discovered bugs within the app). A supplemental visit may be scheduled to review changes associated with app updates.

Once a participant exits the study, either from early exit or completion of study-related activities, an effort will be made to connect them with a managing physician for post-study consultation, instructions and, if indicated, recommendations for follow-up care. The exit workflow will be designed in consultation with the Principal Investigator on this study and with the partnering physician based on clinical best practices. For example, the exit workflow includes an attempt by the managing physician to reach out to the participant's primary care provider to inform them of the study and to provide clinical recommendations. Upon exiting the study, participants will also be provided with key data collected during the study in an "Exit Packet", such as their Sleep Report and prescription for PAP therapy. A supplemental visit may be scheduled for final instruction and recommendations for follow-up care.

Participants will lose access to the VSA app after 90 days of active participation has ended.

6.3. Test Procedures and Data Collection

[REDACTED]

[REDACTED]

[REDACTED]

[REDACTED]

[REDACTED]

[REDACTED]

[REDACTED]

[REDACTED]

[REDACTED]

[REDACTED]

[REDACTED]
[REDACTED]
[REDACTED]
[REDACTED]
[REDACTED]
[REDACTED]
[REDACTED]
[REDACTED]
[REDACTED]
[REDACTED]

[REDACTED]
[REDACTED]
[REDACTED]
[REDACTED]
[REDACTED]
[REDACTED]
[REDACTED]
[REDACTED]
[REDACTED]
[REDACTED]

[REDACTED]

[REDACTED]

[REDACTED]
[REDACTED]
[REDACTED]
[REDACTED]
[REDACTED]
[REDACTED]
[REDACTED]
[REDACTED]
[REDACTED]
[REDACTED]

[REDACTED]

[REDACTED]
[REDACTED]
[REDACTED]
[REDACTED]
[REDACTED]
[REDACTED]
[REDACTED]
[REDACTED]
[REDACTED]
[REDACTED]
[REDACTED]
[REDACTED]
[REDACTED]
[REDACTED]
[REDACTED]

[REDACTED]
[REDACTED]
[REDACTED]
[REDACTED]
[REDACTED]
[REDACTED]
[REDACTED]
[REDACTED]

[REDACTED]
[REDACTED]
[REDACTED]
[REDACTED]
[REDACTED]
[REDACTED]
[REDACTED]
[REDACTED]
[REDACTED]
[REDACTED]

7. Risk Analysis

7.1. Risk Analysis

Verily Life Sciences has conducted an analysis of the benefits and risks of the VSA app.

Verily Life Sciences has determined that this clinical investigation is justified as the overall potential benefit to the population outweighs its risks.

7.2. Benefits

Participants at risk of having OSA will have the opportunity to go through the OSA diagnostic pathway and use a PAP device (if prescribed) at no cost to them.

There are no other benefits to the participants for participating in this study, but the information obtained will be used in scientific research and may be helpful to others in the future.

7.3. Risks

The VSA app is intended to facilitate an Obstructive Sleep Apnea (OSA) management program. It is intended to improve the lives of patients who have been diagnosed with OSA to help manage their therapy and is intended to facilitate a program where users can possibly discover their potential risk for OSA.

The types of potential risk the volunteer research participants will encounter with the VSA app are related to risks for releasing participant/patient private health information. The participant profile in the VSA app will include personal information including name, contact information, and health information, including PAP usage data. All data sent from the VSA app are encrypted. Information collected during interviews from study participants will be kept confidential throughout the study. A unique subject identification code will be used when collecting data on standardized paper or electronic Case Report Forms (CRF/eCRF). Only study team members trained on the clinical study will have access to the study records. If a participant agrees to participate in the study, Verily will store the data collected on Google servers. This data will be restricted to authorized study personnel and access is audited to ensure the privacy of this data. All data used in the analysis and reporting of this study will be used in a manner without identifiable reference to the study participants.

Though PAP is part of the participants' clinical care prescribed by their clinician, for purposes of completeness, potential adverse effects of PAP follow.

1. Skin irritation or rashes
2. Feelings of claustrophobia when wearing mask
3. Dry mouth, throat, or nose after wearing the mask
4. Temporary marks on the skin
5. Difficulty sleeping in the first few weeks of treatment
6. Increased daytime sleepiness in the first few weeks of treatment
7. Bloating
8. Eye irritation
9. Ear or sinus discomfort

Adverse effects/discomfort associated with using PAP and related supplies are considered anticipated and will not be recorded as an adverse event.

Though the HST is part of the participants' clinical care prescribed by their clinician, for purposes of completeness, potential adverse effects of HST follow:

1. Skin irritation
2. Rash
3. Allergic reaction
4. Mild discomfort

Adverse effects/discomfort associated with using an HST and related supplies are considered anticipated and will not be recorded as an adverse event.

There may also be other side effects of participating in this study that are not known at this time.

8. Adverse Events (AE), Serious Adverse Events (SAE), and Unanticipated Problems

During and following a subject's participation in the study, the investigator/institution should ensure that adequate medical care is provided to a subject for any adverse events related to the trial. The investigator/institution should inform a subject when medical care is needed for intercurrent illness(es) of which the investigator becomes aware.

In the event medical care to a subject is required, the medical care given to, and medical decisions made on behalf of, subjects should always be the responsibility of a qualified physician.

8.1. Adverse Events

An Adverse Event (AE) is defined as any untoward medical occurrence, unintended disease or injury in subjects, users or other persons, that is considered a change from baseline or pre-study status, whether or not related to the investigational medical device.

Any pre-existing medical conditions or symptoms present in a participant will not be considered an Adverse Event in this study, unless it worsens as a result of this study.

Only health events that are directly related to the VSA app or study procedures will be recorded as adverse events.

Adverse events related to commercially available FDA-regulated (i.e., cleared or approved) medical devices (such as PAP, HST and associated supplies) will not be recorded as adverse events. Anticipated AEs related to the commercially available FDA-regulated devices include the following:

1. Skin irritation or rashes
2. Feelings of claustrophobia when wearing mask
3. Dry mouth, throat, or nose after wearing the mask
4. Temporary marks on the skin
5. Difficulty sleeping in the first few weeks of treatment
6. Increased daytime sleepiness in the first few weeks of treatment
7. Bloating
8. Eye irritation
9. Ear or sinus discomfort
10. Allergic reaction
11. Mild discomfort

All Adverse Events (AEs) will be reported on an AE Case Report Form and will include the following: Date/time of onset, description of the event, the duration of the event, the severity of the event, assessment of the relation of the event to the study device and procedure, description of action taken (if any) and the event outcome.

In the event medical care to a subject is required, the medical care given to, and medical decisions made on behalf of, subjects should always be the responsibility of a qualified physician.

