8.2. Serious Adverse Events

A Serious Adverse Event (SAE) is defined as an adverse event that is anticipated or unanticipated and which reasonably suggests that one of the manufacturers' devices has or may have caused or contributed to a death or serious injury.

A Serious Adverse Event is an Adverse Event that led to: (a) death, (b) serious deterioration in the health of the subject that either resulted in a (i) life-threatening illness or injury or (ii) permanent impairment of a body structure or a body function, or (iii) in-patient or prolonged hospitalization or (iv) medical or surgical intervention to prevent life-threatening illness or injury or permanent impairment to a body structure or a body function or (c) fetal distress, fetal death or a congenital abnormality or birth defect.

A planned hospitalization for a pre-existing condition is not considered a SAE.

These events are typically reportable to health authorities. Serious Adverse Events must be reported to the sponsor within 24 hours of knowledge of the event.

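### Sections 7.3 and 8.1 bar recording of PAP- and HST-related effects with no exception for serious ones, and 8.2 and 8.3 do not say whether PAP and HST are covered

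*Combined protocol and SAP*

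**What the plan says.** Section 8.1 defines an adverse event broadly, "whether or not related to the investigational medical device", and then narrows what is written down: "Only health events that are directly related to the VSA app or study procedures will be recorded as adverse events". It next says that adverse events related to commercially available, FDA-regulated "medical devices (such as PAP, HST and associated supplies) will not be recorded as adverse events", and lists 11 anticipated effects.

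Section 7.3 has a matching sentence after its list of PAP effects, "Adverse effects/discomfort associated with using PAP and related supplies are considered anticipated and will not be recorded as an adverse event", and another after its list of HST effects, "Adverse effects/discomfort associated with using an HST and related supplies are considered anticipated and will not be recorded as an adverse event".

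Section 8.2 describes an SAE in two ways. It is "defined as an adverse event that is anticipated or unanticipated" that points to an unspecified manufacturer's device as a possible cause of death or serious injury. It is also described by outcome: "A Serious Adverse Event is an Adverse Event that led to: (a) death, (b) serious deterioration in the health of the subject". The duty that follows is "Serious Adverse Events must be reported to the sponsor within 24 hours of knowledge of the event".

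Section 8.3 covers serious effects associated with a device, unnamed, where the effect had not already been identified in kind, severity or frequency. It sets the same 24-hour limit, has the sponsor report SAEs and UADEs to the regulator, and has a Medical Monitor review serious and unanticipated effects. The glossary repeats both definitions.

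**The concern.** The exclusion is written for routine discomfort, but its wording reaches any effect of PAP or HST, however severe. The sections that should catch a serious event do not say whether these devices are in scope. Two members of staff could therefore handle the same serious event differently, each with a section of the protocol to cite.

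At stake is the handling of a possible death, hospitalization or life-threatening reaction in people newly started on PAP, or tested at home, through a remote program. The regulatory report and the Medical Monitor review in 8.3 depend on how the event was classified, so an event stopped at 8.1 may reach neither.

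**Working it through.** The plan gives no figure to reproduce and no arithmetic beyond counts applies. The check sets the sections side by side.

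1. **Exclusion sentences.** 7.3 has two (PAP, HST) and 8.1 has one: 2 + 1 = 3. Sentences with an exception for serious events: 0 of 3. Each 7.3 sentence follows a list of mostly minor effects, but none of the three is confined to the listed items.

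2. **Serious-event texts.** 8.2, 8.3 and the glossary entries for SAE and UADE: 1 + 1 + 2 = 4. Texts that name PAP, HST or the VSA app: 0 of 4. Texts that say whether the 8.1 exclusion carries over: 0 of 4.

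3. **Link between the two sets.** 8.2 makes an SAE a kind of adverse event. A reader who takes 8.1 as settling what is handled as an adverse event can stop there and never ask whether the event was serious.

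4. **One hypothetical event traced through the text.** Suppose a participant is hospitalized after an allergic reaction to HST supplies.
   - Under 7.3 and 8.1 the event is HST-related and allergic reaction is listed, so it is not recorded.
   - Under 8.2 it does not matter that the reaction was anticipated, and hospitalization meets the outcome test. If the HST is a covered device, the event goes to the sponsor within 24 hours.
   - Under 8.3 allergic reaction is listed with no grade, so a severe one could count as not previously identified in severity. If the HST is a covered device, the 24-hour limit again applies.

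5. **Both readings of scope leave a problem.** If PAP and HST are covered, the plan requires a serious event to be reported while telling staff not to record it, and does not explain how the two fit. If they are not covered, sections 7 to 9 state no recording route for a serious PAP- or HST-related event. Section 9 sends PAP malfunctions and complaints to the equipment provider and does not mention the HST.

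6. **Who is affected.** The PAP exclusion applies to the planned 50-200 participants who begin PAP. The HST exclusion can reach more, because the Protocol Summary says that more people will be screened than enrolled. These are numbers exposed, not expected events.

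**The case against.** The strongest reply is that leaving an event unrecorded is not the same as leaving it unreported. 8.1 still calls these occurrences adverse events and only keeps them off the form. The 8.2 duty is a report to the sponsor, and its definition takes in anticipated events. A plan may skip routine recording for marketed devices prescribed as clinical care and still require serious-event reports. This stands as a possible reading, so it would be too strong to say that 8.1 flatly contradicts 8.2. But the plan does not say that this reading is intended.

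Second, a reader might infer that serious PAP or HST events are definitely shut out of safety reporting. The documents do not support that. The definitions in 8.2 and 8.3 are broad enough to include both devices. Section 11.1 requires the investigator to notify the IRB of important safety findings other than SAEs as well. Section 7.3 closes by allowing for side effects of participation that are not yet known.

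Third, a reader might argue from the HST row in Table 1 that the HST is a study procedure and its effects are therefore recordable. That does not help, because 8.1 names the HST in the exclusion itself. Nor can scope be settled from the product description in 10.1, part of which is redacted.

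Fourth, the sponsor could close the gap by declaring that 8.2 and 8.3 cover the app only and naming another route for marketed devices. That would settle the scope. Unless the other route included recording and review, however, serious events in these participants would remain outside both. Operational rules may also sit in the Monitoring Plan, the CRF completion guidelines or the risk files, which are not available here; the protocol text should still be clear by itself.

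**Conclusion.** The concern holds as an unresolved gap between sections. Three exclusion sentences carry no exception for serious events, and four serious-event texts do not say whether PAP and HST are covered. The same serious event could be left unrecorded and unreported, or reported within 24 hours, depending on which section is applied.

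The conclusion goes no further than that. It is not shown that such events are definitely excluded, or that any would be missed. No event rate can be derived. The visible primary and secondary endpoints (timelines, completion and compliance) are not affected. The finding rests on 7.3, 8.1 to 8.3, section 9, 11.1 and the glossary as supplied. Section 6.3 and part of 10.1 are redacted and nothing is inferred from them. Confidence is moderate. The change is worth making because it is cheap and concerns serious safety events.

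**What to change.** Reconcile 7.3, 8.1, 8.2, 8.3 and the glossary:

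1. Limit the three exclusion sentences (two in 7.3, one in 8.1) to non-serious PAP and HST effects.
2. Amend the 8.1 sentence that confines recording to events directly related to the app or study procedures in the same way. Otherwise it could still bar a serious PAP or HST event after step 1.
3. State in 8.2, 8.3 and the glossary which devices are covered. State also that serious PAP- or HST-related events of which the study team becomes aware are recorded on the existing AE form and assessed under those sections.

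Non-serious PAP and HST effects stay unrecorded, as now.

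The cost is a protocol wording change plus some added AE-form entries and reports, whose number cannot be derived from the documents. No new participant contact is needed: Table 1 already schedules adverse event evaluation in 6 of its 6 columns.

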8.2. Serious Adverse Events

A Serious Adverse Event (SAE) is defined as an adverse event that is anticipated or unanticipated and which reasonably suggests that one of the manufacturers' devices has or may have caused or contributed to a death or serious injury.

A Serious Adverse Event is an Adverse Event that led to: (a) death, (b) serious deterioration in the health of the subject that either resulted in a (i) life-threatening illness or injury or (ii) permanent impairment of a body structure or a body function, or (iii) in-patient or prolonged hospitalization or (iv) medical or surgical intervention to prevent life-threatening illness or injury or permanent impairment to a body structure or a body function or (c) fetal distress, fetal death or a congenital abnormality or birth defect.

A planned hospitalization for a pre-existing condition is not considered a SAE.

These events are typically reportable to health authorities. Serious Adverse Events must be reported to the sponsor within 24 hours of knowledge of the event.

